9 STATISTICAL CONSIDERATIONS

9.1 STATISTICAL HYPOTHESES

No formal statistical hypothesis has been formulated. All analyses will be descriptive in nature and no inferential statistical analyses are planned.

9.2 SAMPLE SIZE DETERMINATION

The study plans to enrol 120 patients: 40 will be assigned to the dexamethasone group, 40 to the levofloxacin group and 40 to the dexamethasone-levofloxacin combination.

The sample size has been estimated based on the expected precision (i.e. width of the 95% confidence interval) of the estimates of the study drug concentrations.

For assessment of dexamethasone concentration:

When the sample size is 40, a two-sided 95% confidence interval for a single mean will extend 4.648 ng/ml from the observed mean, assuming that the standard deviation is known to be 15 ng/ml ²⁵ and the confidence interval is based on the large sample z statistic.

For assessment of levofloxacin concentration:

When the sample size is 40, a two-sided 95% confidence interval for a single mean will extend 61.676 ng/ml from the observed mean, assuming that the standard deviation is known to be 199.022 ng/ml²⁶ and the confidence interval is based on the large sample z statistic.

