Before cataract surgery, a limbal paracentesis will be performed and an aqueous humour sample of approximately 0.05 ml will be drawn from the anterior chamber with a 30-gauge needle insulin syringe. The aqueous humour will be stored immediately in vials at -80 °C and subsequently analysed at a central laboratory. Vial labels will contain the kit number but no information regarding the drug received. Laboratory analysts will thus be blinded to the drug administered and samples will be analysed for the concentration of all three molecules (levofloxacin, dexamethasone 21-phosphate and dexamethasone) by means of LC-MS-MS.

Following surgery, patients will be treated with antibiotics and/or steroids according to local clinical practice.

Sample size calculation

[figure not shown]
The study plans to enrol 120 patients: 40 will be assigned to the dexamethasone group, 40 to the levofloxacin group and 40 to the dexamethasone-levofloxacin combination.

The sample size has been estimated based on the expected precision (i.e. width of the 95% confidence interval) of the estimates of the study drug concentrations.

Assessment of dexamethasone concentration: When the sample size is 40, a two-sided 95% confidence interval for a single mean will extend 4.648 ng/ml from the observed mean, assuming that the standard deviation is known to be 15 ng/ml and the confidence interval is based on the large sample z statistic.

	Assessment of levofloxacin concentration: When the sample size is 40, a two-sided 95% confidence interval for a single mean will extend 61.676 ng/ml from the observed mean, assuming that the standard deviation is known to be 199.022 ng/ml and the confidence interval is based on the large sample z statistic.
Drug analysis	All biological samples will be sent to the central laboratory, Ticinumlab, Novara (Italy), which will perform in one run the LC-MS-MS (triple quadrupole) analyses for the simultaneous determination of levofloxacin, dexamethasone and dexamethasone 21-phosphate.
Statistical considerations	Continuous data will be summarized with standard descriptive statistics (i.e. the mean, standard deviation, minimum, median and maximum, 95% confidence limits). Categorical data will be summarized by frequencies and percentages. All analyses will be performed using SAS version 9.4 or later.

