6.1.2 DOSING AND ADMINISTRATION

Eligible patients will be randomly assigned to one of the three following treatment groups in a 1:1:1 ratio:

- Levofloxacin 5 mg/ml + dexamethasone 1 mg/ml (test drug): two 30 μ l doses, 30 minutes apart, one 90 \pm 15 minutes prior to surgery and the other 60 \pm 15 minutes prior to surgery.
- Levofloxacin (Oftaquix[®]): two 30 μ l doses, 30 minutes apart, one 90 \pm 15 minutes prior to surgery and the other 60 \pm 15 minutes prior to surgery.
- Dexamethasone (Tamesad®): two 26 μ l doses, 30 minutes apart, one 90 \pm 15 minutes prior to surgery and the other 60 \pm 15 minutes prior to surgery

Administration of study drugs will be performed by qualified health care personnel using a micropipette and dispenser. Doses are to be administered at the lateral canthus while applying pressure at the medial canthus to prevent drainage of the study drug.

Should the treatment schedule not be respected, subjects will not undergo aqueous humour extraction and will be followed for safety purposes only.

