7 STUDY INTERVENTION DISCONTINUATION AND PARTICIPANT DISCONTINUATION/WITHDRAWAL

7.1 DISCONTINUATION OF STUDY INTERVENTION

If a patient receives only one dose of the study drug (but not the second), this does not mean discontinuation from the study, however aqueous humour will not be extracted from patients if the treatment schedule is not respected. These patients will be followed for safety purposes only. If a clinically significant finding is identified after enrolment, the investigator or qualified designee will determine if any change in participant management is needed. Any new clinically relevant finding leading to discontinuation from study treatment will be reported as an adverse event (AE).

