7.2 PARTICIPANT DISCONTINUATION/WITHDRAWAL FROM THE STUDY

Participants are free to withdraw from participation in the study at any time upon request. An investigator may discontinue or withdraw a participant from the study for the following reasons:

- Pregnancy.
- If any clinical adverse event (AE) or other medical condition or situation occurs such that continued participation in the study would not be in the best interest of the participant.
- If the participant meets an exclusion criterion (either newly developed or not previously recognized) that precludes further study participation.

The reason for participant discontinuation or withdrawal from the study will be recorded on the eCRF. Subjects who sign the informed consent form and are randomized but do not complete the study will not be replaced.

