9.4 STATISTICAL ANALYSES

9.4.1 GENERAL APPROACH

Continuous data will be summarized with standard descriptive statistics (i.e. the mean, standard deviation, minimum, median and maximum, 95% confidence limits). Categorical data will be summarized by frequencies and percentages.

Missing values will not be replaced.

All statistical tables, listings and analyses will be produced using SAS® release 9.4 or later (SAS Institute, Inc., Cary, NC, USA).

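### Does it matter that the half-widths behind n=120 assume a known SD, z and 40 sampled patients per arm?

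*Combined protocol and SAP*

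**What the plan says.** Section 9.2 of the protocol plans 120 patients, 40 assigned to each arm, and gives the width of the 95% confidence interval as the reason for that number. For dexamethasone, "a two-sided 95% confidence interval for a single mean will extend 4.648 ng/ml from the observed mean", and the condition is stated in the same sentence: "assuming that the standard deviation is known to be 15 ng/ml", with the large-sample z statistic. For levofloxacin, with an SD of 199.022 ng/ml taken as known, "a two-sided 95% confidence interval for a single mean will extend 61.676 ng/ml from the observed mean". The synopsis repeats both statements on the same footing ("Assessment of levofloxacin concentration: When the sample size is 40").

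Other sections bear on whether 40 concentrations per arm will exist:

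- Section 6.1.2: "Should the treatment schedule not be respected, subjects will not undergo aqueous humour extraction".
- Section 7.1, which covers patients given only one dose: "aqueous humour will not be extracted from patients if the treatment schedule is not respected".
- Section 7.2: patients who "are randomized but do not complete the study will not be replaced".
- Section 9.4.1: "Missing values will not be replaced".

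Sections 9.4.1 and 9.4.2 promise a mean, an SD and 95% confidence limits by treatment group. They do not say whether the limits use z or t. Section 9.1 states that there is no formal hypothesis and that the analysis is descriptive.

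**The concern.** Precision is the only argument offered for the sample size. There is no power calculation or decision rule, so the two half-widths carry the whole justification. They appear to describe a different situation from the one planned, in two ways.

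First, the SD will not be known. It will be estimated from each arm's data, and an interval that allows for this uses t and is wider. Second, 40 is the number assigned, while the concentration summary can use only patients who were sampled. The protocol itself foresees randomised patients with no sample, does not replace them and does not impute their values, yet neither Section 9.2 nor the synopsis makes any allowance for them. Both dosing windows are counted back from surgery, so a delayed operation could put a patient outside the schedule.

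If the gap were large, the sponsor would have justified the trial on precision it could not deliver, and the case for 40 rather than some larger number per arm would be weak.

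**Working it through.** **Inputs.** SD 15 ng/ml (dexamethasone) and 199.022 ng/ml (levofloxacin), n = 40 per arm, two-sided 95%, all from Section 9.2. The documents give no rate of unsampled patients, so any rate below is an assumption.

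**1. The plan's own figures.** Half-width = z × SD / √n, with z = 1.95996 and √40 = 6.3246.

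- Dexamethasone: 1.95996 × 15 / 6.3246 = 4.648 ng/ml.
- Levofloxacin: 1.95996 × 199.022 / 6.3246 = 61.676 ng/ml.

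Both reproduce to the third decimal.

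**2. Estimated SD, all 40 sampled.** Half-width = t(0.975, n−1) × SD / √n, with t on 39 degrees of freedom = 2.0227.

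- Dexamethasone: 2.0227 × 15 / 6.3246 = 4.797 ng/ml, or 0.149 wider.
- Levofloxacin: 2.0227 × 199.022 / 6.3246 = 63.650 ng/ml, or 1.974 wider.

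The ratio is 2.0227 / 1.95996 = 1.032, so both are 3.2% wider. This sets the sample SD equal to the planned SD. Under normality the average sample SD is slightly lower, and the expected t half-widths are 4.767 and 63.24 ng/ml, about 2.5% above the stated values.

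**3. Fewer than 40 sampled (assumed rates).**

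| Unsampled (assumed) | n per arm | t-based half-width, dex / levo (ng/ml) | Against stated |
|---|---|---|---|
| 0% | 40 | 4.80 / 63.65 | +3.2% |
| 5% | 38 | 4.93 / 65.4 | +6.1% |
| 10% | 36 | 5.08 / 67.3 | +9.2% |
| 20% | 32 | 5.41 / 71.8 | +16.3% |

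Loss alone, keeping z, has a smaller effect: at n = 36 the factor is √(40/36) = 1.054, giving 4.90 and 65.0 ng/ml (+5.4%).

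**4. How much the realised width varies anyway.** Assume normal data and a true SD of exactly 15 ng/ml. The realised t half-width at n = 40 is then 4.797 × √(χ²/39). With χ² at its 2.5% and 97.5% points on 39 degrees of freedom (23.65 and 58.12), the central 95% range is 4.797 × 0.779 = 3.74 to 4.797 × 1.221 = 5.86 ng/ml. The 0.149 ng/ml shift from z to t is small beside a range about 2.1 ng/ml wide.

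**5. Does any criterion fail?** Section 9.2 gives an expected precision and sets no maximum width. Section 9.1 rules out inferential analysis. Neither a 3% nor a 9% wider interval crosses a limit in the documents, because there is none.

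**The case for a change.** The strongest argument for acting is that disclosure is only partial. Section 9.2 is open about the known SD and about z. It does not say that the figures need every assigned patient to be sampled, while Sections 6.1.2, 7.1 and 7.2 create a route by which some will not be. When precision is the sole rationale, it should describe the analysis that will be run, and the remedy would cost only a few words. With t, 43 sampled patients per arm would be needed to reach the stated half-widths. Under normality, with the true SD as planned, the realised t interval at n = 40 would exceed the stated width about 58% of the time.

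Part of this stands. Forty is the assigned number, and a sentence saying so would be tidier. The rest carries less weight:

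- The 43 treats the stated half-widths as targets, and the protocol does not set them as targets.
- The 58% needs a comparator. With z and an estimated SD the figure is already 47%, since a random width falls above its planning value about half the time. Using t adds about 11 percentage points.
- The larger widenings depend on loss rates that nothing in the documents supports. Section 1.3 places randomisation at the pre-dose visit on the day of surgery, staff give both doses and log the times (Sections 6.1.2 and 6.4), and participation ends in the operating room (Section 4.1). Section 5.4 sees no need for a retention strategy in so short a study. Loss may well be low, though this cannot be shown from the documents.

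**Conclusion.** The concern is numerically right but does not call for a change. The half-widths of 4.648 and 61.676 ng/ml are exact for 40 patients, a known SD and z, and they are slightly favourable as forecasts. The one effect that needs no assumed loss rate is about 3%: 4.80 and 63.65 ng/ml with 40 sampled patients per arm, taking the planned SDs as correct and assuming the final limits are t-based. Unsampled patients would add to that by an unknown amount, with a combined increase of about 9% if 10% were lost.

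Nothing downstream depends on the difference. The sample size stays at 120, no target width is missed, no test is run, and the report will show the limits obtained with the SD and the number of patients observed. Leaving z or t unnamed in Section 9.4.1 is a gap that analysts fill sensibly: with an estimated SD and about 40 observations, t is the ordinary choice. Unsampled patients have no concentration to summarise, so the n behind each mean is also clear. Writing either point down would record normal practice and would alter no result or conclusion.

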9.3 POPULATIONS FOR ANALYSES

The descriptive analysis will be carried out on the following populations:

- Per Protocol (PP): all patients who have completed the study without any major protocol deviations.
- Full analysis Set (FAS): all randomized patients. According to Intention To Treat (ITT) principles all patients will be analyzed considering the randomized study treatment assigned by IWRS.

The safety analysis will be performed on the Safety Population, made up of all patients who have received at least one dose of study treatment.

9.4 STATISTICAL ANALYSES

9.4.1 GENERAL APPROACH

Continuous data will be summarized with standard descriptive statistics (i.e. the mean, standard deviation, minimum, median and maximum, 95% confidence limits). Categorical data will be summarized by frequencies and percentages.

Missing values will not be replaced.

All statistical tables, listings and analyses will be produced using SAS® release 9.4 or later (SAS Institute, Inc., Cary, NC, USA).

9.4.2 ANALYSIS OF THE ENDPOINT

Aqueous humour concentration of levofloxacin and dexamethasone, measured by LC-MS-MS, will be descriptively summarized by treatment group and 95% confidence limits will be provided.

9.4.3 SAFETY ANALYSES

The incidence of Adverse Events (AEs) and Serious Adverse Events (SAEs) recorded throughout the study will be presented overall and by treatment group respectively.

Depending on the onset date of the event, AEs will be defined as follows:

- Treatment-emergent AEs, those events with an onset date after any treatment initiation.
- Non-treatment-emergent AEs, those events with an onset date between informed consent and any treatment initiation.

Non-treatment-emergent AEs will be listed only.

Sponsor: NTC S.r.l.

Version 1.0

Protocol No.: LevoDesa_05-2017 21 March 2018

Treatment-emergent AEs will be summarized using the Medical Dictionary for Regulatory Activities (MedDRA) System Organ Class (SOC) and Preferred Term (PT). A summary of treatment-emergent AEs by SOC, PT and severity will be also provided. All related treatment-emergent AEs, treatment-emergent AEs with an outcome of death, treatment-emergent AEs leading to discontinuation of treatment will be summarized by MedDRA SOC and PT and will also be listed.

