1.2 STUDY DESIGN

1.3 SCHEDULE OF ACTIVITIES (SOA)

		Day of surgery			
Procedures	Screeninga	Pre-dose	First dose	Second dose	Limbal
		Pre-dose	-90 (±15) min	-60 (±15) min	Paracentesis
Informed consent	Χ				
Demographics	Χ				
Medical history	Χ				
Concomitant medications	Χ	Χ			
Pachymetry	Χ				
Fluorescein test	Χ				
Inclusion/Exclusion	Х	Х			
criteria	Χ	Α			
Pregnancy test ^b		Χ			
Randomization		Χ			
Study drug administration ^c			Х	X	
Limbal paracentesis					Х
Administration of					Х
Mydrane ^{®d}					^
Adverse event review and	Х	Х	Х	X	Х
evaluation ^e	^	^	^	^	^

^a Screening must take place not more than 28 days prior to surgery.

^b Urine pregnancy test (women of childbearing potential).

 $^{^{\}rm c}$ Two doses 30 minutes apart, the first 90 (\pm 15) minutes prior to surgery, and the second 60 (\pm 15) minutes prior to surgery.

^d Mydrane[®] is to be administered following withdrawal of aqueous humour.

^e Adverse events are to be reported until 7 (for non-serious AEs) or 30 days (for SAEs) after the last day of study participation.

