2.2 BACKGROUND

Cataract is an ocular condition that causes vision impairment due to changes in the opacity of the ocular lens. Cataract is an age-related condition, but smoking, ocular trauma, exposure to ultraviolet light, diabetes and drug induced metabolic changes in the lens are risk factors for lens opacification causing cataract.¹

The only cure for cataract is surgical, with phacoemulsification with lens implantation as the treatment of choice.² Recovery after surgery is easier than it was in the past and patients usually no longer require in-patient hospital care, with recovery usually uneventful and pain-free. However, adverse events may occur due to corneal trauma, ocular inflammation and dryness, which can result in ocular irritation during the recovery period.³⁻⁵ These conditions may cause symptoms such as pain, burning, stinging, foreign body sensation, itchiness and glare in the operated eye. The incidence of ocular irritation symptoms experienced during the first postoperative hours may be as high as 98%.⁶ Conjunctival hyperaemia, anterior chamber cells and flare and cystoid macular oedema are some possible signs of inflammation after cataract surgery.

In many cases, inflammation is self-limiting, but drug therapy is often used to shorten resolution time and improve ocular comfort.⁷

Steroidal and non-steroidal anti-inflammatory drugs are used to prevent and treat postoperative inflammation. Topical corticosteroids are usually administered for 1 to 6 weeks after cataract surgery. According to the practice pattern studies published by the American Society of Cataract Refractive Surgery (2012), Canadian Ophthalmological Society members study 2011⁸ and European Society of Cataract and Refractive Surgeons (ESCRS), there are variations in postoperative drug therapy provided to individual patients and among different countries. In Europe, dexamethasone was the most commonly used steroidal anti-inflammatory drug and was chosen as the preferred drug by 71% of ophthalmological surgeons.⁹

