4 STUDY DESIGN

4.1 OVERALL DESIGN

This is a randomized, assessor-blinded, parallel-group clinical study.

One hundred and twenty (120) patients scheduled for cataract surgery at 2 centres who have provided written informed consent will undergo screening procedures during a preoperative visit. Prior to surgery, and once eligibility criteria have been confirmed, eligible patients will be assigned to one of the three following treatment groups in a 1:1:1 ratio:

- Levofloxacin 5 mg/ml + dexamethasone 1 mg/ml (test drug)
- Levofloxacin (Oftaquix®)

• Dexamethasone (Tamesad®)

Administration of study drugs will be performed by qualified health care personnel using a micropipette and dispenser. Two doses of one of the study treatments will be administered, the first 90 ± 15 minutes prior to surgery, and the second 60 ± 15 minutes before surgery. The two doses must be administered 30 minutes apart. Eye drops are to be administered at the lateral canthus while applying pressure at the medial canthus to prevent drainage of the drug.

Phacoemulsification and limbal paracentesis will be performed by an experienced surgeon. Before the main incisions of phacoemulsification, approximately 0.05 ml of aqueous humour will be drawn from the anterior chamber with a 30-gauge needle syringe. Mydrane[®], a combined solution (phenylephrine [0.31%], tropicamide [0.02%] and lidocaine [1%]) for intracameral injection indicated for cataract surgery to obtain mydriasis and intraocular anaesthesia during the surgical procedure is to be administered following paracentesis. The patient's participation in the study will end with the administration of Mydrane[®]. Following surgery, patients will be treated with antibiotics and/or steroids according to local clinical practice.

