8.4 ADVERSE EVENTS AND SERIOUS ADVERSE EVENTS

8.4.1 DEFINITION OF ADVERSE EVENTS (AE)

An adverse event can be defined as any untoward medical occurrence associated with the use of an intervention in humans after providing written informed consent for participation in the study until the end of study visit, whether considered intervention-related or not.

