8.4.4 TIME PERIOD AND FREQUENCY FOR EVENT ASSESSMENT AND FOLLOW-UP

The occurrence of an adverse event (AE) or serious adverse event (SAE) may come to the attention of study personnel during study visits and interviews of a study participant presenting for medical care, or upon review by a study monitor.

All AEs including local and systemic reactions will be captured on the appropriate case report form (eCRF). Information to be collected includes event description (a diagnosis and not symptoms should be provided, if possible), time of onset, clinician's assessment of severity, relationship to study product (assessed only by those with the training and authority to make a diagnosis), and time of resolution/stabilization of the event. All AEs occurring while on study must be documented appropriately regardless of relationship. All AEs will be followed to adequate resolution.

Any medical condition that is present at the time that the participant is screened will be considered as baseline and not reported as an AE. However, if the study participant's condition deteriorates at any time during the study, it will be recorded as an AE.

Changes in the severity of an AE will be documented to allow an assessment of the duration of the event at each level of severity to be performed. AEs characterized as intermittent require documentation of onset and duration of each episode.

The investigator will record all reportable events with onset dates occurring any time after informed consent is obtained until 7 (for non-serious AEs) or 30 days (for SAEs) after the last day of study participation. Events will be followed for outcome information until resolution or stabilization.

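### The treatment-emergent AE table in section 9.4.3 is not split at surgery, so surgical and aftercare events dilute any arm difference in how the drops are tolerated

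*Combined protocol and SAP*

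**What the plan says.** Section 9.4.3 defines the main safety category: "Treatment-emergent AEs, those events with an onset date after any treatment initiation". It gives no end to the window and no division at surgery. These events are tabulated by arm, by MedDRA class and term, and by severity. Related treatment-emergent events get their own summary and listing. Under section 8.3, adverse events are the whole of the safety assessment.

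The timing comes from three places:

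- Section 4.1 sets the doses as "the first 90 ± 15 minutes prior to surgery, and the second 60 ± 15 minutes before surgery". The patient's "participation in the study will end with the administration of" the intracameral mydriatic, given after the aqueous humour sample.
- Section 8.4.4 collects events "until 7 (for non-serious AEs) or 30 days (for SAEs) after the last day of study participation", and footnote e of the schedule of activities (section 1.3) agrees.
- Section 8.4.1 instead ends the definition of an adverse event with the words "until the end of study visit, whether considered intervention-related or not". The schedule contains no such visit.

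On other drugs, section 4.1 says: "Following surgery, patients will be treated with antibiotics and/or steroids according to local clinical practice". The schedule row "Concomitant medications" is marked at screening and pre-dose only. Section 6.5 requires concomitant drugs in the eCRF without giving a stop time, and section 9.4.4 tabulates them by arm.

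On background symptoms, section 2.2 says: "The incidence of ocular irritation symptoms experienced during the first postoperative hours may be as high as 98" per cent.

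**The concern.** The symptoms that section 2.2 attributes to surgery, such as burning, stinging and foreign-body sensation, are those that a reaction to an eye drop could plausibly produce. Section 9.4.3 counts both in the same rows. A reader comparing the combination with its single components on tolerability would be looking at event rates that come mainly from the operation and its aftercare.

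The aftercare adds a second difficulty. Post-operative antibiotics and steroids belong to the same classes as the study drugs. If they are not recorded while events are still being collected, a later irritant or allergic event cannot be set against what the patient was then receiving, and nobody can check whether aftercare was balanced between arms.

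Safety is not the objective of this trial, but this table is its whole safety output.

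**Working it through.** **The plan's own figures.** The documents give no calculation for safety. Their only design calculation is the confidence-interval half-width for mean concentration with 40 patients per arm (section 9.2). It reproduces: 1.96 × 15/√40 = 4.648 ng/ml and 1.96 × 199.022/√40 = 61.676 ng/ml. The present point does not depend on it.

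**Step 1: share of the window before surgery.** The inputs are m = 75, 90 or 105 minutes from first dose to surgery (section 4.1) and D = 7 or 30 days of collection afterwards (section 8.4.4). The share is m/(m + 1440·D).

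- 7 days: 90/(90 + 10,080) = 0.88%, with range 75/10,155 = 0.74% to 105/10,185 = 1.03%.
- 30 days (serious events): 90/(90 + 43,200) = 0.21%, with range 0.17% to 0.24%.

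This is a share of clock time, not of events.

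**Step 2: what pooling does to an arm difference.** Let b be the chance that a patient has a surgical event of the kind in question, equal in all arms. Let d₁ and d₀ be the drug-caused risks in two arms, independent of b. Then P(any event) = 1 − (1 − b)(1 − d), and the pooled difference is (1 − b)(d₁ − d₀). With 40 per arm, the 95% half-width is 1.96·√[(p₁(1 − p₁) + p₀(1 − p₀))/40].

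All values of d, and b = 20% and 50%, are assumptions. The value 98% is the upper figure in section 2.2. Entries are the difference in percentage points, with the half-width in brackets.

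| Drug-caused risk | b = 0 (before surgery) | b = 20% | b = 50% | b = 98% |
|---|---|---|---|---|
| 10% vs 0% | 10 (9) | 8 (19) | 5 (22) | 0.2 (6) |
| 20% vs 5% | 15 (14) | 12 (20) | 7.5 (22) | 0.3 (6) |
| 30% vs 5% | 25 (16) | 20 (20) | 12.5 (21) | 0.5 (6) |

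For example, at 10% vs 0% and b = 20%: p₁ = 1 − 0.8 × 0.9 = 28%, p₀ = 20%, the difference is 8 points, and the half-width is 1.96·√[(0.2016 + 0.16)/40] = 19 points. In that first row, a 20% background doubles the half-width (9 to 19) while the difference shrinks. The normal approximation is rough where a risk is 0% or close to 100%.

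The b = 0 column is an idealisation in two ways. It assumes that drug-caused events start before surgery, and it ignores the anaesthetic and povidone-iodine allowed in the last 10 minutes (section 5.2, criterion 8).

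**Step 3: date or time.** Section 9.4.3 classifies by onset date. In the schedule, the pre-dose check, both doses and surgery fall on one day, so a date cannot place an event before or after the first drop, or before or after surgery. Section 8.4.4 already collects time of onset, and section 6.4 has administration times written in the Dose and Sampling Log.

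**The case against.** The strongest reply is that nothing is biased. Allocation is randomised 1:1:1 and stratified by centre, every arm has the same surgery, and aftercare follows the centre. The analysis is descriptive (section 9.1), and the objective is penetration into the aqueous humour. Section 9.4.3 also plans a summary and listing of related events, and section 8.4.3.2 bases relatedness partly on timing. Much of this stands, and it rules out several stronger readings that a reader might infer:

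- **That the table shows surgery instead of the drops.** The documents do not support this. A shared background shrinks the arm difference and widens its interval, but does not replace it. Aftercare would bias the difference only if it differed by arm, and nothing shows that it would.
- **That about 39 of 40 patients per arm will have an irritation event (0.98 × 40).** The 98% is an upper figure for symptoms, not a rate of recorded events. No post-operative study visit is scheduled, and section 8.4.4 prefers a diagnosis to symptoms. The 98% column is therefore an extreme, and the point rests on the 20% and 50% columns.
- **That post-operative drugs go unrecorded.** Section 6.5 has no time limit, so recording is unclear, not excluded.
- **That drug exposure lasts only 90 minutes.** Section 2.2 says drug is still detectable 12 hours after dosing, so a delayed reaction could start after surgery.

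The related-event table is only a partial substitute. Relatedness is judged by the site clinician, while the only blinding described is that of the laboratory analyst (sections 4.2 and 6.3). The category of unknown relationship is allowed, and section 9.4.3 does not say how it is counted. A cut by time of onset needs no such judgment.

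**Conclusion.** The point holds as a matter of presentation and precision. The treatment-emergent window in section 9.4.3 has no cut at surgery, and under the 7-day rule about 99% of it lies after surgery. Overall rates will therefore mostly describe surgery and aftercare, and any arm difference in tolerability of the drops will be diluted by the factor (1 − b). For an assumed 10% versus 0%, that means 10 points before surgery, 8 at a 20% background and 5 at 50%, with half-widths of about 9, 19 and 22 points.

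The size rests on assumed drug risks and backgrounds, on independence of the two, and on event terms that surgery also produces. For a term that surgery does not produce, b is near zero and little is lost. It also rests on the 7/30-day rule. If section 8.4.1 were read as stopping collection when participation ends, most of the post-operative window would disappear. No sample size or formal comparison changes. The change is worth making because it is cheap and uses an objective cut.

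**What to change.** 1. In section 9.4.3, keep the overall treatment-emergent table and add one by arm, split by onset before and after the start of surgery. Start of surgery is a better cut than paracentesis, because patients whose dosing schedule was not respected have no aqueous humour taken (section 6.1.2).
2. Classify by clock time, using the onset time in section 8.4.4 and the dosing times in the Dose and Sampling Log. The protocol does not expressly list the start time of surgery as collected; if it is not, add that one field.
3. Flag events that start after the anaesthetic and povidone-iodine in the last 10 minutes before surgery. Show the post-surgery period by arm too, because drug may persist for 12 hours.
4. Reconcile the concomitant-medication row of the schedule with section 6.5, so that post-operative antibiotics and steroids are recorded through the AE collection window.
5. Reconcile the end of the AE period in section 8.4.1 with the 7/30-day rule in section 8.4.4 and footnote e of the schedule.

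The cost is one extra table, slightly more data entry on an existing medication record, and possibly one time field.
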